The proposed study will be the first randomized controlled clinical trial that will investigate the use of d-PTFE membrane compared to Ti-mesh in vertical augmentation. The study will be able to provide scientific evidence that will help clinicians in the decision-making process for vertical ridge augmentation. The split-mouth study design will support a direct comparison between the two surgical techniques. Additionally, this project will benefit TUSDM educationally by creating more interest in the vertical ridge augmentation procedure among the residents, dental students and faculty members. Ultimately, it may improve the quality of care for the patients at TUSDM.

The current literature does not provide evidence-based criteria that indicate one of the two techniques currently used in the clinic. The primary goal of this study is to compare the efficacy by measuring clinical height gain between the two techniques. The secondary goal of the study is to compare the morbidity with patient-centered outcomes research design. The proposed study will help make more informed treatment decisions of patients by providing evidence on the risks and benefits between the treatment options.

TUSDM Periodontology Clinic Standard of Care

A patient who requires vertical ridge augmentation receives either of the two surgical materials, d-PTFE membrane or Ti-mesh, based on the dentist's preference. It is the surgeon's discretion to choose one or the other material based on their experience. The two materials are considered equally effective and no additional risk of one over the other has been reported at TUSDM.

III) Research Plan

A) Experimental Design

The proposed study design is a randomized controlled trial, split mouth design, to compare the two different vertical augmentation procedures: Titanium mesh (Ti-mesh) technique and Guided Bone Regeneration (GBR) technique with a high-density polytetrafluoroethylene (d-PTFE) membrane.

B) Sample Size and Statistical Analysis

Sample Size:

We have used the available data (mean, standard deviation) for the height gain with an anorganic bovine bone (Bio-oss) with e-PTFE membrane or Ti-mesh for the sample size calculation.^{6,15} We anticipate that the property of a d-PTFE membrane is similar to an e-PTFE membrane, and the amount of the height gain to be similar between these two membranes.¹⁰

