A power calculation was performed in nQuery Advisor (version 7.0) with the following assumptions: a type I error of 5%; a type II error of 7%; the titanium mesh group has a mean (SD) height gain of 5.2 (0.79) mm (Artzi 2003)¹⁵; the e-PTFE group has a mean (SD) height gain of 3.15 (1.12) mm (Simion 2007)⁶. The minimum sample size necessary was determined to be 7 subjects. To account for potential dropout, the study population will be increased to include 10 subjects. Up to 15 subjects will be consented (and considered enrolled) into the study to achieve these goals.

Statistical Analysis:

Counts and percentages, will be reported for categorical data. Mean and standard deviations will be reported for continuous data.

1. For the Aim 1, the height gain will be measured in millimeters (mm) and considered to be continuous data. The paired t-test will be used to compare the height gain after the healing following vertical ridge augmentation between the d-PTFE membrane group and the Ti-mesh group.

2. For the Aim 2, the mean incidence of post-operative complication in each group will be measured in percentage as categorical data. The Mann-Whitney U test will be used to compare the incidence of post-operative complications occurred in vertical ridge augmentation procedures between the d-PTFE membrane group and the Ti-mesh group.

3. For the Aim 3, the new bone formation will be measured in percentage as categorical data. The paired t-test will be used to compare the percentage of

new bone formation after the healing following vertical ridge augmentation between the d-PTFE membrane group and the Ti-mesh group.

All analyses will be performed using Stata (version 13.1)

Randomization:

Randomization will be performed in a 1:1 ratio using a balanced design based on a computer-generated randomization scheme, both for the location of the procedure, but also for the performed technique. Randomization will occur during visit 2.

Blinding:

The subjects will be blinded for the randomization assignment (Single-blinded). We will blind subjects by not informing them of their treatment allocation (d-PTFE membrane or Ti-mesh). If subjects do not see the preparation of the materials (d-PTFE or Ti-mesh), they will not be able to tell which procedure they receive. The preparation of d-PTFE membrane and Ti-mesh will be performed and delivered to the surgical site out of sight of participants during surgery.

C) Products

Group	Product 1	Product 2

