 - patient currently taking steroid medication
 - history of oral bisphosphonate intake greater than 3 years or any IV administration
- (4) Pregnant or lactating patients (self-reported), as part of TUSDM standard of care not to treat for non-emergency surgical procedures
- (5) Presence of surgical scar tissue from previous surgical procedure in the posterior mandible
- (6) Pathology present within the alveolar ridges in the posterior mandible, determined clinically or radiographically
- (7) History of radiation therapy to the mandible
- (8) Smokers

Elective periodontal procedures are postponed during pregnancy, active infectious disease, bisphosphonate intake or uncontrolled diabetes as standard of care in the TUSDM department of periodontology. Diseases or conditions which have been shown to affect healing are excluded for research. Vertical ridge augmentation is not contraindicated with pregnancy and there is no known safety issues associated with it.

3) Subject Withdrawal/Termination Criteria

- (1) Non-compliance.
- (2) Unwillingness to further participate.

The Principal Investigator will determine whether withdrawn subjects are in need of additional treatment and/or follow-up observation as a result of participation in this trial. These treatment and/or follow-up appointments will follow standard clinic guidelines of the TUSDM periodontology clinic dependent upon which point the subject was withdrawn from the study.

D) Assessment

1) Risk

The present study has no additional risks to the subjects beyond the normal risks for the surgical procedure as the study involves standard clinical procedures performed at TUSDM periodontology clinic. However, subjects may experience more discomfort and longer surgery time because two surgeries will be done in one day for this study. Usually, either of one augmentation techniques is used at a time for one side from standard clinical practice at TUSDM, because vertical augmentation is technically demanding procedure. However, occasionally, we perform two vertical augmentation procedures at a time for both sides depending on cases in the practice or at TUSDM.

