The pre-operative height of the bony crest will be evaluated on the pre-existing radiographs from the referring clinic if they are less than 6 months old. If recent radiographs do not exist, radiographs will be taken at this visit. Regardless of the subject's involvement in the study, it is standard of care to have radiographs taken within the past 6 months prior to surgery.

Visit 2: Surgery

Medical history will be reviewed as standard of care.

Eligibility and subject withdrawal criteria will be reviewed to ensure the subject still qualifies for the study.

Surgeries will be performed by either of two investigators.

The use of d-PTFE for vertical ridge augmentation will be randomly assigned to one side of the mouth of each subject (randomization is for research purposes) and Ti-mesh to the other side of mouth, and therefore, subjects will receive both of the following procedures:

*Guided Bone regeneration (GBR) procedure using a d-PTFE: (standard of care excluding clinical measurements)

The following steps will be performed following standard of care procedures: local anesthesia, muco-periosteal incision, full thickness flap reflection, de-cortication of the alveolar ridge, bone harvesting using bone scrapers, tenting screw placement, clinical measurements, DBBM graft material placement, the placement and stabilization of the d-PTFE membrane according to manufacturer's instructions, sutures.

* Guided Bone regeneration (GBR) procedure using Ti-mesh: (standard of care excluding clinical measurements)

The following steps will be performed following standard of care procedures: local anesthesia, muco-periosteal incision, full thickness flap reflection, de-cortication of the alveolar ridge, bone harvesting using bone scrapers, tenting screw placement, clinical measurements, DBBM graft material placement, the placement and stabilization of the titanium mesh according to manufacturer's instructions, sutures.

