For research, information regarding bleeding, presence of infection, bruising, and/or other complications will be collected. Each subject will complete a survey to evaluate the level of pain/discomfort, bleeding, and swelling following the surgical procedure for each side – each classified on a VAS scale from zero to ten. In addition, the subject will return his or her completed medication log.

Visit 4 (21±3 days after procedure): Post-operative Follow-up

Medical history will be reviewed as standard of care. Eligibility and subject withdrawal criteria will be reviewed to ensure the subject still qualifies for the study.

Each subject will have a post-operative visit, which is standard practice at TUSDM periodontology clinic. Standard of care procedures including suture removal and evaluation of surgical site will be performed.

For research, information regarding bleeding, presence of infection, bruising, and/or other complications will be collected. Each subject will complete a survey to evaluate the level of pain/discomfort, bleeding, and swelling following the surgical procedure for each side – each classified on a VAS scale from zero to ten.

Follow-up visits during the six month post-operative period of the vertical ridge augmentation surgery will be scheduled. Standard of care procedures and evaluations will be completed during follow-up visits. The surgical sites will be evaluated after the vertical ridge augmentation procedures, in order to assess the presence of postoperative complications, such as the exposure of a d-PTFE membrane or Ti-mesh, infection, swelling, paresthesia or any other complications. All will be noted in the subject's axiUm record and reviewed at the time of Visit 4.

Visit 5 (6±1 months after Visit 4): Evaluation visit

Medical history will be reviewed as standard of care. Eligibility and subject withdrawal criteria will be reviewed to ensure the subject still qualifies for the study.

Surgical sites will be evaluated and the subject's axiUm record will be reviewed for any complications.

Each subject will complete a survey to evaluate the level of pain/discomfort, bleeding, and swelling following the surgical procedure for each side – each classified on a VAS scale from zero to ten, as at Visit 3.

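### Aim 2 compares complications with the Mann-Whitney U test, which treats the two sides of one mouth as independent samples; a paired analysis is needed.

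*Combined protocol and SAP*

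**What the plan says.** All references are to the combined protocol and SAP.

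- **Design.** In III.E, Visit 2, d-PTFE is "randomly assigned to one side of the mouth of each subject (randomization is for research purposes) and Ti-mesh to the other side of mouth". Section III.D (Assessment, Risk) adds that "two surgeries will be done in one day for this study". The Rationale gives the reason for this design: "The split-mouth study design will support a direct comparison between the two surgical techniques".
- **Aim 2 analysis (III.B, Statistical Analysis, item 2).** The endpoint is described as follows: "the mean incidence of post-operative complication in each group will be measured in percentage as categorical data". The test is then named: "The Mann-Whitney U test will be used to compare the incidence of post-operative complications occurred in vertical ridge augmentation procedures".
- **Aims 1 and 3 (items 1 and 3).** Both use a paired test. For Aim 1: "The paired t-test will be used to compare the height gain after the healing following vertical ridge augmentation".
- **Standing of Aim 2.** The Rationale says: "The secondary goal of the study is to compare the morbidity with patient-centered outcomes research design".

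Nowhere do the documents give a paired test, a mixed model, GEE or any other allowance for the pairing in Aim 2.

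**The concern.** Each subject supplies one observation to each technique, from the same mouth, operated on the same day. The Mann-Whitney test assumes two independent samples. For a yes/no complication per side, its p-value depends only on the two totals; it cannot use the information on which complications fell in the same mouth.

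If complications tend to occur together in a mouth, the test overstates the variance of the difference, becomes too conservative and can miss a real difference in morbidity. If they tend to avoid each other, its error rate can exceed 5%. Either way the error rate is governed by a correlation that the test ignores. At stake is the inference on the trial's stated secondary goal.

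**Working it through.** **The plan's own figure.** The only sample size is 7 subjects, for Aim 1. With a difference of 5.2 − 3.15 = 2.05 mm and pooled SD √((0.79² + 1.12²)/2) = 0.969, a two-sided 5% two-sample t-test has power 0.909 at 6 and 0.952 at 7, so 7 is the smallest number reaching the planned 93%. There is no sample size, power or assumed rate for Aim 2 to reproduce.

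**Inputs for Aim 2.** From the documents: 10 subjects planned, 7 as the minimum, one side per technique. Assumed, because the documents are silent: the incidences and the within-mouth correlation (phi).

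**Step 1. Why the pairing matters.** With n pairs and common incidence p, the difference between the two totals has variance 2np(1 − p)(1 − phi). The Mann-Whitney variance in effect sets phi to 0.

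**Step 2. Same totals, different pairings.** Take 7/10 v 3/10 sides with a complication.

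*Mann-Whitney.* U = 70, with expectation 50. Tie-corrected variance = (100/12) × [21 − 1980/380] = 131.6. So z = 20/11.47 = 1.74 and p = 0.081, however the sides pair up.

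*McNemar.* If k subjects have complications on both sides, the discordant pairs are b = 7 − k and c = 3 − k, and the asymptotic statistic is (b − c)²/(b + c) on 1 df. The paired risk difference is (b − c)/10 = 0.40 throughout. Its score 95% CI is the set of values D not rejected by the paired score test; at D = 0 that test is asymptotic McNemar.

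| Both sides (k) | b v c | Statistic | Asymptotic p | Mid-p | Exact p | Score 95% CI |
|---|---|---|---|---|---|---|
| 3 | 4 v 0 | 16/4 = 4.00 | 0.046 | 0.0625 | 0.125 | 0.01 to 0.69 |
| 2 | 5 v 1 | 16/6 = 2.67 | 0.10 | 0.125 | 0.219 | −0.09 to 0.72 |
| 0 | 7 v 3 | 16/10 = 1.60 | 0.21 | 0.227 | 0.344 | −0.21 to 0.78 |

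The paired evidence differs across the three rows; the planned p-value does not.

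**Step 3. True type I error at nominal 5%.** Full enumeration of the four outcomes per subject (both sides, d-PTFE only, Ti-mesh only, neither), 10 pairs. The probability of both is p² + phi·p(1 − p); for p = 0.4 and phi = 0.375 this is 0.16 + 0.09 = 0.25, leaving 0.15 for each discordant cell.

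| Incidence, both techniques | phi | Mann-Whitney | Asymptotic McNemar | Mid-p |
|---|---|---|---|---|
| 40% | 0 | 4.0% | 5.3% | 2.5% |
| 40% | 0.375 | 1.1% | 3.3% | 0.78% |
| 40% | 0.583 | 0.26% | 1.3% | 0.18% |
| 30% | −0.43 | 7.8% | 4.8% | 3.4% |

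The last row is an extreme: −0.3/0.7 = −0.43 is the lowest phi possible at 30% incidence, where no subject ever has complications on both sides.

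**Step 4. Power at 60% v 20%.**

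| Pairs | phi | Mann-Whitney | Asymptotic McNemar | Mid-p | Exact |
|---|---|---|---|---|---|
| 10 | 0.3 | 40% | 56% | 37% | 18% |
| 10 | 0 | 42% | 42% | 34% | 20% |
| 8 | 0.3 | 35% | 40% | 19% | 6% |
| 7 | 0.3 | 31% | 30% | 11% | 2% |

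**Step 5. If each side has a count or score.** Normal model, 10 pairs, 20,000 simulated trials, 1 SD shift for power. At correlation 0.5, Mann-Whitney has size 1.2% and power 57%; signed-rank has size about 5% and power 78%. At correlation 0, power is 55% and 49% respectively.

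**The case against.** The strongest reply accepts the mismatch and disputes its consequence. For a yes/no outcome the power advantage belongs to asymptotic McNemar alone, the most liberal version. In the 4 v 0 example its p of 0.046 rests on four discordant pairs; mid-p gives 0.0625 and exact 0.125. Mid-p is more conservative than the planned test at positive correlation (0.78% v 1.07% at 40% incidence, phi 0.375) and can have less power: at 50% v 20%, phi 0.3, 10 pairs, it has 17% against 21% for Mann-Whitney. The gain also needs nearly full retention. Positive correlation is a judgement, since exposure or paresthesia may be largely local to one site. Finally, Aim 2 is secondary and unpowered, and the likely error is conservative.

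Most of this stands as a limit on what pairing can deliver in 7 to 10 subjects, and it bears on which paired test to choose. It does not rescue the planned test, whose error rate depends on a correlation it ignores. Nor is conservatism harmless in a comparison of morbidity, where a missed difference may be read as reassurance. The paired risk difference and its interval do not depend on the choice among McNemar versions.

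It is also true that item 2 does not say whether incidence means any complication per side, a count, or each type separately. That has to be settled, because it decides which paired test applies.

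**Conclusion.** The concern holds. The test named for Aim 2 does not match the split-mouth design or the paired tests used for Aims 1 and 3, and nothing elsewhere corrects it. With positive within-mouth correlation, which a shared mouth and surgery day make plausible, it is conservative: 1.1% true size at phi 0.375 and 40% incidence. In the yes/no scenarios with 10 pairs, it exceeds 5% only under negative correlation.

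The power loss against asymptotic McNemar is 16 points (56% − 40%) at 60% v 20%, phi 0.3 and 10 pairs, and nil at zero correlation or with 7 pairs. All these figures rest on assumed incidences and correlations. The point should be fixed because it affects the stated secondary goal; it does not affect Aim 1 or the sample size.

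**What to change.** In III.B, item 2:

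1. Define the per-side variable: any complication (yes/no), or a count or score.
2. For yes/no, make the paired risk difference with its score 95% CI the main Aim 2 result. Support it with McNemar's test in one version fixed in advance. Asymptotic is the better choice: it agrees with the score interval, and mid-p can be more conservative than the test being replaced. Keep the exact version as a sensitivity analysis only.
3. For a count or score per side, use the Wilcoxon signed-rank test.

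**Cost.** One sentence for the test, plus the definition of the variable. No new data are needed if the complication form records the side. This should be confirmed: the surveys are explicitly per side, but for the clinician's record at Visits 3 and 4 the text says only that "information regarding bleeding, presence of infection, bruising, and/or other complications will be collected".

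**Downsides.** Asymptotic McNemar can slightly exceed 5% (5.3% at phi 0, 40% incidence). Exact McNemar needs at least six discordant pairs, all in one direction (2 × 0.5⁶ = 0.031; five give 0.0625). With so few pairs, the interval should carry the interpretation.

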Bone harvesting using bone scrapers will be performed during GBR procedures with both techniques (d-PTFE and Ti-mesh). Bone harvesting using bone scrapers is for harvesting particulate autogenous bone graft material. We will use a mixture of 50:50 DBBM and autogenous bone graft material for all vertical augmentation procedures in the study. Particulate autogenous bone graft will be harvested from the retromolar region of the mandible. This area is just next to the area of GBR procedures (posterior mandible) and will be visible after flap elevation for vertical augmentation. Therefore, we do not need any additional steps except harvesting autogenous bone graft. Intraoral harvesting by bone scrapers from the retromolar region is a simple and safe method for collecting cortical bone chips.

The intrasurgical clinical measurements of the ridge height will be taken during surgery. The distance between the top of the tenting screw and bone crest will be measured with a periodontal probe during the procedure.

Duration of each procedure and surgical complications including flap tear and bleeding will be collected. All outcome measurements will be performed by a Co-I who did not perform the surgery.

The subject will be asked to complete a pain/discomfort survey using VAS scale from zero to ten. A medication log will be given to the patient to track the number of pills of the prescribed painkiller they have taken in order to examine the amount of pain after the surgical procedures. The mean number of pills used after surgical procedures will be analyzed.

Post-operative medication will be prescribed following TUSDM standard of care guidelines.

Visit 3 (7±3 days after procedure): Post-operative Follow-up

Medical history will be reviewed as standard of care. Eligibility and subject withdrawal criteria will be reviewed to ensure the subject still qualifies for the study.

Each subject will have a post-operative visit, which is standard practice at TUSDM periodontology clinic. Standard of care procedures including suture removal and evaluation of surgical site will be performed.

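### The plan neither sets nor records which technique is operated first on the shared surgery day, so order could follow technique and bias the paired comparison

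*Combined protocol and SAP*

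**What the plan says.** **What is randomised.** Section III.B, Randomization: "Randomization will be performed in a 1:1 ratio using a balanced design based on a computer-generated randomization scheme". The sentence goes on to name two items: "both for the location of the procedure, but also for the performed technique". On timing: "Randomization will occur during visit 2".

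**How it is carried out.** Section III.E, Visit 2: "The use of d-PTFE for vertical ridge augmentation will be randomly assigned to one side of the mouth of each subject", with Ti-mesh going to the other side. No step in that section sets a sequence.

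**Same day.** Section III.D, Assessment, Risk: "two surgeries will be done in one day for this study". The same paragraph expects longer surgery, and says that one side at a time is usual because the operation is technically hard.

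**Operators and blinding.** Visit 2: "Surgeries will be performed by either of two investigators". Only subjects are blinded (Section III.B, Blinding).

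**Data and analysis.** Visit 2: "Duration of each procedure and surgical complications including flap tear and bleeding will be collected". Order is not among the items listed there, nor in Table 1. Height gain is compared by a paired t-test with no order term.

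**The concern.** With two sides, two techniques and both used in every subject, the side that gets d-PTFE fixes the side that gets Ti-mesh. Location and technique are therefore a single binary draw. If the second item in Section III.B means something more, such as which side or technique goes first, the plan does not say so.

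That leaves same-day order open. The operator must know the allocation to operate, and nothing stops one technique from usually going first. The plan itself describes the surgery as demanding and the day as long, so some difference between the first and second side is plausible.

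If order follows technique, the paired difference estimates the technique effect plus the order effect. This applies to height gain, the primary efficacy measure. It applies more directly to procedure duration, flap tear and bleeding. If order is not recorded, the bias can be neither checked nor adjusted for afterwards.

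**Working it through.** **Inputs from Section III.B, Sample Size.** Ti-mesh 5.2 (SD 0.79) mm; e-PTFE, standing in for d-PTFE, 3.15 (SD 1.12) mm; type I error 5%; type II error 7%; minimum 7 subjects, raised to 10. The test is taken as two-sided, since sidedness is not stated.

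**The plan's own figure.** Planned difference: 5.2 − 3.15 = 2.05 mm. Pooled SD: √((0.79² + 1.12²)/2) = 0.969 mm. A two-sample t-test has 90.9% power at 6 per group and 95.2% at 7, so 7 is the smallest number reaching 93%. The stated 7 reproduces, and this point does not dispute it.

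**SD of the paired difference.** √(0.79² + 1.12² − 2ρ × 0.79 × 1.12). This is 1.37 mm at ρ = 0 and 1.00 mm at ρ = 0.5. The plan gives no correlation, so both are assumptions.

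**Bias.** Let π be the height gain on the first side minus that on the second, other things equal, and p the share of subjects with Ti-mesh first. Each Ti-mesh minus d-PTFE difference is shifted by +π when Ti-mesh goes first and by −π when it goes second. The mean shift is (2p−1)π. The documents give no value for π, so 0.5 mm is assumed, with a range of 0.25 to 1.0 mm.

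| Ti-mesh first | 2p−1 | π = 0.25 | π = 0.5 | π = 1.0 |
|---|---|---|---|---|
| 10 of 10 | 1.0 | 0.25 mm (12%) | 0.50 mm (24%) | 1.00 mm (49%) |
| 8 of 10 | 0.6 | 0.15 mm (7%) | 0.30 mm (15%) | 0.60 mm (29%) |
| 5 of 10 | 0 | 0 | 0 | 0 |

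Percentages are of 2.05 mm.

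**False rejection when the techniques do not differ (n = 10, two-sided 5%).**
- All 10 with the same technique first: 8% to 11% at 0.25 mm, 18% to 29% at 0.5 mm, 54% to 81% at 1.0 mm. The lower figure is for SD 1.37, the higher for SD 1.00.
- An 8:2 split at 0.5 mm: 8% to 11%, by simulation of 400,000 trials. The simulation includes the extra spread that mixed order adds to the differences.

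**Power at the planned effect.** A full 0.5 mm bias against Ti-mesh leaves 2.05 − 0.5 = 1.55 mm. Power at n = 10 is then 89% (SD 1.37) or 99% (SD 1.00).

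**Order left to chance.** The probability of 8:2 or worse in either direction among 10 subjects is 2 × (45 + 10 + 1)/1024 = 10.9%.

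**Can 10 subjects be balanced?** Write the four cells as a (d-PTFE right, Ti-mesh first), b (d-PTFE right, d-PTFE first), c (d-PTFE left, Ti-mesh first) and d (d-PTFE left, d-PTFE first). Side is 5:5 if a + b = 5. Technique order is 5:5 if a + c = 5. Together these give b = c and a = d. The right side goes first in b + c = 2b subjects, which cannot equal 5. So a = 3, b = 2, c = 2, d = 3 balances side and technique order and leaves the first-operated side at 4:6. With additive side and order effects, that imbalance does not enter the technique difference.

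**Cost of an order term.** With order 5:5 at n = 10, residual degrees of freedom fall from 9 to 8. Power for 2.05 mm is 98.4% at ρ = 0 (98.7% unadjusted) and above 99.9% at ρ = 0.5. With 7 subjects split 4:3, adjusted power is 87.5% or 98.8%.

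**The case against.** **The plan may already randomise order.** Section III.B names two randomised items. If the second is not redundant, it may mean which side or technique goes first. This stands: a reader might infer that the plan randomises side only, by design, and the text does not establish that. But it does not establish randomised order either, and Visit 2 contains no such step. The wording needs settling on either reading.

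**Confounding is hypothetical.** It needs order to follow technique. If the same side always went first and side allocation were balanced 5:5, p would be one half and the bias zero. This also stands, although no such rule is written.

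**The mechanism is thin.** Local anaesthesia is listed separately for each procedure, so nothing suggests that the second side depends on the first side's anaesthetic. Height is measured by a co-investigator who did not operate. The plan mentions longer surgery as a burden on the subject, not as a threat to bone gain. This weakens the case for a large effect on height. It does less for duration and intra-operative complications.

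**Surgeon tied to technique.** A reader might also infer that the two investigators could each take a side. The Visit 2 text on operator and measurer, with the Personnel section, reads more naturally as one operator per subject, so the documents do not support that as a finding. Recording the operator is enough.

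**Conclusion.** The point holds as a gap in the design. Same-day order is not specified, not recorded and not in the analysis, and Section III.B is unclear against Visit 2. An operator who knows the allocation could let order follow technique, and the paired t-test would carry any resulting bias in full.

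The size depends on two unknowns: the order effect (assumed 0.5 mm, range 0.25 to 1.0) and the split. The bias runs from zero to 0.5 mm at the assumed effect, and to 1.0 mm at the top of the range. The 18% to 29% false rejection is a worst case, with one technique first in every subject, and should not be read as the expected error rate. The documents do not show that confounding will occur, and at the planned 2.05 mm the trial would usually still detect a difference.

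The change is still worth making. It protects the primary comparison at almost no cost, and unrecorded order cannot be recovered at analysis.

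**What to change.** Reword Section III.B, Randomization, and the matching Visit 2 text along these lines: *For each subject, the computer-generated list assigns (a) which side receives d-PTFE and (b) which technique is operated first. Each is balanced 5:5 over the 10 subjects.* One allocation that does this is:

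| | Ti-mesh first | d-PTFE first |
|---|---|---|
| d-PTFE on right | 3 | 2 |
| d-PTFE on left | 2 | 3 |

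Record the order and the operator for each side on the CRF. Add to the Statistical Analysis for Aim 1 a sensitivity analysis that regresses the within-subject difference in height gain on order, coded +1 or −1, and reports the intercept as the technique effect. This also covers imbalance caused by dropout.

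The cost is one extra list column, one or two CRF items and one degree of freedom in the sensitivity analysis. The sample size and visit schedule stay as they are.
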